4.5. Open Label Run-In

For all potentially eligible patients who provide informed consent and declare interest in participation, baseline ALT, AST, hepatitis screens, CrCl, albumin, and CBC will be obtained prior to the 5- to 6-week (maximum 8-week) active run-in phase to ensure they meet trial enrollment criteria. A urine sample will be assayed for albumin and creatinine. A blood sample for plasma and buffy coat will also be shipped to the central lab for long-term storage and to

provide a bank for future blood-based biomarker and genetic sub-studies. Quality of life questionnaires will also be administered.

A 5- to 6-week (maximum 8-week) course of open-label LDM will then be given to all eligible study participants in a pre-randomization compliance and tolerability run-in. During this run-in, participants will be given an initial 5 mg oral weekly LDM dose along with an adequate supply of 1.0 mg folic acid to be taken 6 days per week using similar drug calendar packs to those used throughout the active trial period. In the absence of adverse effects or intolerance, this 5 mg dose will be increased to 10 mg for the second and third week of the run-in phase, and then to 15 mg for the fourth and subsequent weeks. This run-in will allow subjects who are poorly compliant, who develop any immediate side effects, or who withdraw informed consent to be excluded before randomization. Participants must tolerate LDM 15 mg two weeks in a row in order to continue in the trial. All subjects who successfully tolerate LDM 15 mg two weeks in a row and are still willing to be randomized will have repeat blood evaluation for AST, ALT, albumin, CBC, and CrCl, and any individuals with substantive changes in these parameters will be excluded prior to randomization. Urine for albumin and creatinine will also be collected. The run-in will thus enhance long-term compliance and eliminate risk of exposure for any individuals with immediate intolerance to LDM.

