- h. have positive or negative effects on standardized measures of quality of life and global health status

Proposed Exploratory and Mechanistic Studies

Clinical endpoints of interest that will be prospectively evaluated include incident age-related macular degeneration, sleep apnea, and nephropathy and retinopathy. In addition, a plasma and DNA bank will be established as part of the trial protocol. Thus, cohort accrual and biobanking also allows for the evaluation of several exploratory aims that relate to mechanisms of effect using measured plasma biomarkers of inflammation and glucose metabolism, as well as potential genetic determinants of LDM activity. Analyses are planned that will

- a. Evaluate the effect of LDM as compared to placebo on a series of inflammatory biomarkers such as IL-6, TNF, CRP, interleukin-1 (IL-1), and interleukin-1 receptor antagonist (IL1ra), and to ascertain whether any effects on these biomarkers mediate observed benefits or risks of LDM on clinical outcomes in the trial.
- b. Evaluate whether genetic polymorphisms associated with vascular risk, inflammation, thrombosis, or LDM metabolism modify any benefits or risks of LDM on clinical outcomes observed in the trial.
- c. Among subjects with baseline diabetes, evaluate the effect of LDM as compared to placebo on indices of diabetic progression and glycemic control such as need for diabetes treatment intensification, proportion of subjects achieving optimal glycemic control (HbA1c<7.0%), and change in HbA1c overall and by study visit.

Variables for safety assessment will include:

- a. adverse events
- b. transaminase levels
- c. hematology
- d. creatinine clearance
- e. reported symptoms

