4.3. Efficacy

Efficacy analyses of the primary and secondary endpoints of the trial will focus on time from randomization to the first occurrence of the event. These analyses will use a likelihood ratio test based on a proportional hazards model stratified on time since index myocardial infarction (≥ 6 months vs < 6 months) and diabetes mellitus vs metabolic syndrome alone at baseline, to test the null hypothesis of no association between assignment to active methotrexate and the rate of the endpoint. Estimation will use the exact method to handle ties⁴. Although randomization is also stratified by site, we judge the potential loss of information associated with additional stratification on this variable to be a greater concern than any associated gain, so that stratification by site will not be part of the primary analysis. All primary and pre-specified secondary analyses will classify patients according to their randomized treatment assignment, i.e. according to the intention to treat principle, and will base evaluation of statistical significance on a two-sided test with level 0.05. The estimated relative hazard in the methotrexate group compared to the placebo group with an accompanying 95% confidence interval will quantify the treatment effect⁵. If this relative hazard is less than 1, then $100 \times (1 - \text{estimated relative hazard})$ will be defined as the percent reduction in hazard associated with methotrexate treatment.

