We will conduct these subgroup analyses regardless of whether or not the overall analyses of treatment effects are significant. Our approach to interpretation of subgroup analyses has always been very cautious and recognizes that, even in large trials, it is not likely to be possible to identify reliably subgroups of patients in whom treatment is especially effective or ineffective. In the absence of prior evidence for real heterogeneity, the overall trial result may provide the best evidence for the presence of a benefit in a subgroup¹³. Our approach thus corresponds to an informal empirical Bayes procedure in which effects in an outlying subgroup require interpretation in light of the overall treatment effect¹⁴.

The pre-specified secondary endpoints (all-cause mortality, primary endpoint plus coronary revascularization, hospitalization for congestive heart failure, primary endpoint plus all-cause mortality plus coronary revascularization plus congestive heart failure, net clinical benefit or harm, and new onset type 2 diabetes) will be evaluated using the same procedures described above for the primary endpoints. The net clinical benefit or harm endpoint will be presented as a table of the incidence of adverse events occurring with greater than 1% frequency in either treatment group, as well as a test of proportions for comparing the incidence in each treatment group. The overall rate of any serious adverse event during the randomized treatment period will also be compared between the methotrexate and placebo groups. Pre-specified tertiary endpoints will also be evaluated using the same procedures described for the primary endpoint.

Measures of quality of life and global health status, assessed at baseline, 1-year and closeout visits, will be analyzed in a mixed-effects linear regression model with subject as a random effect. Of particular interest in this model will be a time by treatment interaction. The

model will use two indicators of post-randomization (1-year and final visit) to evaluate a possible non-linear effect of treatment on outcomes by time.

To enhance interpretation for clinicians through consideration of absolute treatment effects, we will also estimate the number needed to treat or the number needed to harm, for both primary and secondary endpoints. Specifically, we will use the approach of Altman and Andersen¹⁵ to obtain these estimates based on the Kaplan-Meier estimates of time-specific treatment effects.

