Longitudinal analyses will quantify the impact of methotrexate on biomarkers including lipid levels, inflammatory markers, creatinine, and change in HbA1c, with the latter analyses stratified by presence of diabetes at baseline. Additional longitudinal analyses will evaluate the time course of methotrexate treatment on important biomarkers of safety including serum creatinine and estimated glomerular filtration rate.

Mediation analyses exploring treatment effect differences by achieved reduction in inflammation and level of adherence to assigned treatment are also planned. Following approaches used in previous analyses of the relationship of changes in lipids and hs-CRP with effects of statin therapy on outcomes¹⁶⁻¹⁸, we will group subjects into achieved target levels of biomarkers and relate these achieved levels to treatment outcomes. This will also be combined with an analysis of compliance to explore whether observed treatment effects are compliance driven.

We also plan to evaluate whether genetic polymorphisms associated with vascular risk, inflammation, thrombosis, or LDM metabolism modify any benefits or risks of LDM on clinical outcomes observed in the trial.

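### The SAP's quality-of-life model names only a random subject effect and no baseline adjustment, which gives up precision and can understate the closeout standard error if correlation decays over time.

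*Combined protocol and SAP*

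**What the plan says.** Quality of life and global health status form tertiary aim (h) in SAP section 3.0, which asks whether methotrexate will "have positive or negative effects on standardized measures of quality of life and global health status". SAP section 4.3 gives the analysis:

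- The measures are "assessed at baseline, 1-year and closeout visits" and "will be analyzed in a mixed-effects linear regression model with subject as a random effect".
- The contrast is stated as "Of particular interest in this model will be a time by treatment interaction".
- Time enters as two indicators, one for the 1-year visit and one for the final visit, so that the treatment effect need not be linear in time.

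The paragraph names no residual covariance structure, random slope, robust standard error or baseline covariate. It does not say whether a treatment main effect is included or whether the arms share a baseline mean. SAP section 4.1 calls for stratification of all analyses by time since the index infarction and by diabetes status, but does not mention the baseline score.

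The baseline score precedes randomization. Protocol section 4.5 lists it with the assessments made before the run-in: "Quality of life questionnaires will also be administered".

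**The concern.** Two features of the model matter.

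First, baseline is one of the modelled outcomes and the effect is an interaction. If a treatment main effect is included, as is conventional, each arm has its own baseline mean and the interaction at each visit is the between-arm difference in raw change. Randomization makes the expected baselines equal, so estimating them separately spends information for nothing.

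Second, a random subject effect with independent residuals imposes one correlation on baseline to 1 year, baseline to closeout, and 1 year to closeout. SAP section 1.3 plans 2 to 4 years of follow-up, so the closeout gap is longer than the 1-year gap and varies between participants. If correlation falls with time, the model's single within-subject variance is too small for the closeout contrast and may be too large for the 1-year contrast.

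At stake are the width and calibration of the intervals for aim (h), and the closeout interval above all.

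**Working it through.** The documents give no sample size, standard deviation, effect size or correlation for quality of life, so there is no stated figure to reproduce. The correlations below are assumptions, shown as a range. The calculation takes 1:1 allocation (SAP 1.2), equal variances at the three visits, complete data and large samples. The two-sided 5% level is the one that SAP 4.3 sets for primary and pre-specified secondary analyses ("will base evaluation of statistical significance on a two-sided test with level 0.05"); I assume it here.

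**Precision from baseline adjustment.** Let rho be the correlation between baseline and the visit, with unit variances.

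- Variance of raw change: 2(1 − rho).
- Variance after baseline adjustment: 1 − rho².
- Ratio: (1 − rho²) / [2(1 − rho)] = (1 + rho)/2.

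At rho = 0.5 the ratio is 0.75, equivalent to 1/0.75 = 1.33 times the participants. At rho = 0.7 it is 0.85, or 1/0.85 = 1.18 times. Over rho from 0.3 to 0.8 the ratio runs from 0.65 to 0.90.

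**Calibration of each visit's test.** Write the correlations as a (baseline–1 year), b (baseline–closeout) and c (1 year–closeout), with mean m.

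- The random-intercept model gives every change contrast a variance proportional to 2(1 − m).
- The true variances are proportional to 2(1 − a) at 1 year and 2(1 − b) at closeout.
- Model SE / true SE = sqrt[(1 − m)/(1 − a)] at 1 year and sqrt[(1 − m)/(1 − b)] at closeout.
- Actual type I error = 2Φ(−1.96 × ratio).

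Example, a/b/c = 0.70/0.50/0.60: m = 0.60. Closeout ratio = sqrt(0.40/0.50) = 0.894, type I error 8.0%. One-year ratio = sqrt(0.40/0.30) = 1.155, type I error 2.4%.

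**Joint test of both interaction terms (2 df).** The model covariance is proportional to (1 − m)[[2, 1], [1, 2]]. The true covariance has diagonal 2(1 − a) and 2(1 − b) and off-diagonal 1 − a − b + c. The eigenvalues of (model)⁻¹(true) sum to 2 in every pattern tried, so over- and understatement largely cancel.

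| a / b / c | 1-year SE ratio | 1-year type I | Closeout SE ratio | Closeout type I | Joint type I |
|---|---|---|---|---|---|
| 0.60 / 0.60 / 0.60 | 1.000 | 5.0% | 1.000 | 5.0% | 5.0% |
| 0.60 / 0.55 / 0.65 | 1.000 | 5.0% | 0.943 | 6.5% | 5.1% |
| 0.60 / 0.45 / 0.50 | 1.099 | 3.1% | 0.937 | 6.6% | 5.1% |
| 0.65 / 0.50 / 0.65 | 1.069 | 3.6% | 0.894 | 8.0% | 5.2% |
| 0.70 / 0.50 / 0.60 | 1.155 | 2.4% | 0.894 | 8.0% | 5.3% |
| 0.70 / 0.50 / 0.70 | 1.106 | 3.0% | 0.856 | 9.3% | 5.5% |

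The closeout SE is too small in every decay pattern tried. The 1-year SE is correct in one and too large in the rest.

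**The case against.** The strongest reply is that the SAP is silent rather than wrong. Naming subject as a random effect does not rule out a residual covariance structure or robust standard errors. A treatment main effect is never mentioned, and without one the listed terms would already give the arms a common baseline mean. This stands: free baseline means are the conventional reading, not a stated choice.

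A reader might also infer that the standard errors are wrong at both visits. The documents do not support that. They give no correlations; under equal variances and equal correlations the standard errors are exact, and in one decay pattern the 1-year standard error is still exact. With two time indicators, a joint interaction test is a natural reading of the contrast of interest, though the SAP does not say so, and that test stays close to 5%.

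A reader might further infer that the model discards the baseline. It does not: baseline is in the outcome vector and the change contrast is unbiased. In absolute terms the lost precision is small. At an assumed 3,000 per arm, the SE in standard-deviation units is sqrt[4(1 − rho)/3000] for raw change and sqrt[2(1 − rho²)/3000] after adjustment: 0.026 against 0.022 at rho = 0.5, and 0.020 against 0.018 at rho = 0.7.

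Finally, the same fault might be read into the biomarker analyses. SAP 4.3 says only "Longitudinal analyses will quantify the impact of methotrexate on biomarkers including lipid levels, inflammatory markers, creatinine, and change in HbA1c". It names no model there, so no error is shown.

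What survives is narrower. As written, the paragraph does not secure baseline adjustment or a covariance that fits unequal gaps, and it leaves both open to choice after the data are seen.

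**Conclusion.** The point holds as a low-cost improvement to the analysis of one tertiary endpoint. On the conventional reading, each visit's effect is an unbiased difference in raw change, and baseline adjustment would cut its variance to 0.75 (rho 0.5) to 0.85 (rho 0.7) of its value. If correlation decays towards closeout, a separate closeout test at nominal 5% runs at about 6.5% to 9%, the 1-year test at 5% or below, and the joint test at 5.1% to 5.5%.

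The formulas are firm under equal variances and complete data. The sizes rest on assumed correlations, and the precision loss also rests on a treatment main effect that the SAP does not state. The primary analysis, sample size and stopping rules are untouched.

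**What to change.** Replace the model sentence in SAP 4.3 with a constrained longitudinal model:

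- a baseline mean common to both arms, or the baseline score as a covariate;
- treatment-by-visit effects at 1 year and closeout;
- an unstructured covariance over the three visits.

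The text should also say whether inference is by the joint test or by separate visit contrasts.

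Both the baseline and the covariance change are needed. In a rough simulation (60 replicates, 100 per arm, correlations 0.70/0.50/0.70), a common baseline mean with only a random intercept still gave a closeout model SE of 0.110 against an empirical SD of 0.128.

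The cost is a sentence or two in the SAP and a change of model options. The baseline scores are already collected before randomization, so no further data are required.

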4.15. Central Laboratory and Bio-bank

Blood samples for storage in a bio-bank at Brigham and Women's Hospital will be obtained at the pre-run-in, randomization, and at 8 and 24 months after randomization. Processing and long-term storage of these samples will be done in a liquid nitrogen biobank facility in Boston, which has been used for this purpose in multiple prior NIH-funded trials and large cohort studies. White blood cells from the pre-run-in sample will also be stored in this facility to allow for DNA extraction at a later date. As described in the informed consent documents, participation in the genetic bio-banking portions of CIRT will be on an "opt-out" basis and are not a requirement for participation in the main trial.

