As a consequence of these intended changes, the anticipated trial sample size was reduced from 7,000 to 5,500 and the targeted number of primary endpoints (now MACE-plus) was increased from 530 to 634 to have 90% power to detect a 23% reduction in the hazard of MACE-plus. However, while approved by the NHLBI External Advisory panel, the formal amendment to alter the protocol had yet to be submitted for IRB approval at the time of the first formal IDSMB meeting occurred to address efficacy and futility (upon accrual of half of the required MACE and MACE-plus endpoints) on March 13, 2018. At that meeting, the IDSMB recommended early termination of the trial based on crossing a pre-specified boundary for futility and absence of evidence for reduction in hsCRP with LD-MTX treatment. The IDSMB further asked for a formal safety follow-up visit for all participants after an additional 6 months of follow-up. These recommendations were accepted by the NHLBI in April 2018.

For the above reasons, the original Statistical Analysis Plan for the trial did not undergo formal revision (and is presented in full below). However, to be consistent with investigator intent and actions taken by the IDSMB, both the MACE and MACE-plus endpoints are presented in the primary report.

Statistical Analysis Plan

Cardiovascular Inflammation Reduction Trial (CIRT):

A randomized, double-blind, placebo-controlled, event-driven trial of weekly low-dose methotrexate (LDM) in the prevention of recurrent cardiovascular events among stable post-myocardial infarction patients with type 2 diabetes or metabolic syndrome

**Center for Cardiovascular Disease Prevention
Brigham and Women's Hospital**

Funding: National Heart Lung and Blood Institute

March 25, 2013

Abbreviations

ALT	Alanine aminotrasferase
AST	Aspartate aminotransferase
CIRT	Cardiovascular Inflammation Reduction Trial
CRP	C reactive protein
DSMB	Data Safety and Monitoring Board
HbA1c	Hemoglobin A1c
HDL-C	High density lipoprotein cholesterol
ITT	Intention to Treat
LDM	Low dose methotrexate
LDL-C	Low density lipoprotein cholesterol
MACE	Major Adverse Cardiovascular Event
NHLBI	National Heart Lung and Blood Institute
SAE	Serious adverse event
SD	Standard deviation
WBC	White blood cell count

Table of Contents

1.0. STUDY DETAILS	4
1.1. Study Objectives	4
1.2. Study Design	4
1.3. Number of Subjects	5
2.0. ANALYSIS SETS	6
2.1. Definition of Analysis Sets	6
2.2. Violations and Deviations	6

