While all primary and secondary endpoint analyses are on an intention-to-treat basis, CIRT is also functioning as a proof of concept trial and thus secondary analyses of those compliant with the respective LDM or placebo regimens will also be conducted. These analyses will use time-varying proportional hazards models, with an individual's level of adherence updated at each study visit. Adherence will be examined on a time-varying basis using a metric based on percent of study drug taken at last visit, such as half or more vs. less than half, and will also be analyzed cumulatively. Similar analyses will also be conducted on the basis of plasma levels of LDM metabolism.

We will explore in subgroup analyses whether treatment effects vary across categories of baseline covariates including age, gender, race, presence of diabetes or metabolic syndrome at baseline, index MI ≤ 6 vs > 6 months prior, baseline lipid levels, CHF at baseline, baseline inflammatory biomarker levels including high-sensitivity C-reactive protein, revascularization status, baseline background treatments including those known to affect adenosine, such as aggrenox, methylxanthines, and fioricet, nutritional measures related to adenosine function such as estimated daily total caffeine intake, and by plasma measures of LDM metabolism. Cutpoints for analyses will be determined after the final distribution of patients has been established.

Within each subgroup, we will use proportional hazards models to estimate the relative rate of the primary endpoint associated with active treatment versus placebo. Both crude analyses and models including limited baseline covariates will be fitted. To test for the significance of modification of treatment effects by a baseline characteristic, we will include interaction terms between this characteristic and treatment in the proportional hazards model, with statistical significance determined by a likelihood ratio test comparing models with and without the interaction terms between treatment and the categories of a specific covariate.

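### SAP 4.3 names neither a baseline covariate nor a baseline sample for the biomarker and HbA1c analyses, although one of the two pre-randomization samples follows open-label methotrexate

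*Combined protocol and SAP*

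**What the plan says.** SAP 4.3 covers the biomarkers in one sentence: "Longitudinal analyses will quantify the impact of methotrexate on biomarkers including lipid levels, inflammatory markers, creatinine, and change in HbA1c". The HbA1c part is split by diabetes status at entry. Protocol 5.6 says much the same. Neither names a model, a transformation, a baseline covariate or a reference sample. The general rule in SAP 4.1 stratifies by time since the index infarction and by diabetes or metabolic syndrome, which is not adjustment for a participant's own biomarker value. Quality of life, by contrast, gets a named mixed-effects model in SAP 4.3.

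For inflammatory markers, SAP 3.0 sets a between-arm aim: "Evaluate the effect of LDM as compared to placebo on a series of inflammatory biomarkers". For HbA1c in participants with diabetes it lists "change in HbA1c overall and by study visit", next to two outcomes that are not change scores (control below 7.0% and treatment intensification). It does not say from which measurement change is counted.

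Under protocol 4.15, bio-bank samples "will be obtained at the pre-run-in, randomization, and at 8 and 24 months after randomization". Between the first two, everyone takes open-label methotrexate for 5 to 6 weeks (at most 8). Protocol 4.5 adds: "Participants must tolerate LDM 15 mg two weeks in a row in order to continue in the trial".

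Two further analyses in SAP 4.3 depend on a starting value: subgroups by "baseline inflammatory biomarker levels including high-sensitivity C-reactive protein", and a mediation analysis that refers to how far inflammation has fallen.

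**The concern.** Two things are left open. The first is precision. A participant's own earlier value usually predicts the later one, and a value taken before randomization is a valid covariate. A change score, or a follow-up level with no adjustment, gives up precision that samples already banked could supply.

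The second is the origin for change. The pre-run-in sample is untreated and the randomization sample is not. If the latter serves as baseline, any effect reached during the run-in is already in it. The methotrexate arm then shows too small a fall, and placebo shows a rise as the drug is withdrawn.

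This matters because target engagement governs how a null cardiovascular result is read: as evidence against the inflammatory hypothesis, or as a drug that did not lower inflammation in this population. The Introduction placed before the SAP records that the monitoring board, besides a crossed futility boundary, cited "absence of evidence for reduction in hsCRP with LD-MTX treatment".

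**Working it through.** The plan gives no standard deviation, correlation or precision for these analyses, so there is no figure of its own to reproduce. Inputs from the documents are 3,500 per arm (SAP 1.3), two-sided α = 0.05 (SAP 4.3, stated for primary and secondary endpoints and assumed here), and the sampling times above. Assumed inputs are equal variances (SD = 1) and a correlation r between repeated values.

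**Precision.** Variance per participant, in units of σ²:
- Change score: 2(1−r)
- Adjusted for one baseline: 1−r². The ratio to the change score is (1+r)/2, a reduction of (1−r)/2.
- Adjusted for two exchangeable baselines: 1−2r²/(1+r). The ratio to the change score is (1+2r)/[2(1+r)].

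| r | Change score | One baseline | Reduction | Two baselines | Reduction |
|---|---|---|---|---|---|
| 0.5 | 1.00 | 0.75 | 25% | 0.667 | 33% |
| 0.6 | 0.80 | 0.64 | 20% | 0.550 | 31% |
| 0.7 | 0.60 | 0.51 | 15% | 0.424 | 29% |

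Over a wider range, the one-baseline reduction runs from 40% (r = 0.2) to 5% (r = 0.9). If the pre-run-in value adds nothing once the randomization value is known (a Markov pattern), the two-baseline reduction falls back to the one-baseline column. If the comparator is an unadjusted follow-up level, one baseline cuts variance by r², which is 25% at r = 0.5 and 49% at r = 0.7.

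**What this means at trial size.** The detectable difference at 90% power is (1.960+1.282)·√(2/3500)·√variance. One-baseline adjustment moves it from 0.0775 to 0.0671 SD at r = 0.5, and from 0.0600 to 0.0553 SD at r = 0.7. Power for a 0.1 SD difference at r = 0.5 goes from 98.7% to 99.8%. With an assumed 1,750 per arm, for example one diabetes stratum, it goes from 84.1% to 92.7%. All assume complete data.

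**Origin for change.** Let D be the true effect and g the share of it already present at randomization. Change from the randomization sample averages (1−g)D on methotrexate and −gD on placebo, so the difference is D for every g. With D = −0.30 SD:

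| g | Methotrexate arm | Placebo arm | Difference |
|---|---|---|---|
| 1 | 0.00 | +0.30 | −0.30 |
| 0.5 | −0.15 | +0.15 | −0.30 |
| 0 | −0.30 | 0.00 | −0.30 |

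A simulation with 3,500 per arm and r = 0.6 agreed with each row to within 0.002. Change from the pre-run-in sample was about −0.30 on methotrexate and 0.00 on placebo for every g. Adjustment for either baseline recovered about −0.30 throughout.

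**What is known about g.** Only its direction. Run-in doses reach 10 mg in week 2 and 15 mg in week 4 (protocol 4.5). Protocol 3.4 describes a rapid effect at 10 to 30 mg weekly, but in rheumatoid arthritis. Protocol 4.1 allows 20 mg from month 4, so some effect could come later.

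**The case against.** The strongest reply is that the plan is silent rather than wrong. A reader might infer that the SAP has chosen an unadjusted analysis, or a raw change score for HbA1c. The text supports neither: a longitudinal model may include baseline, and change analysed with baseline as a covariate gives the same treatment estimate as adjusted level. That part of the reply stands.

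A reader might also infer that about 30% of precision is being lost. That needs a change-score comparator, two baseline values and roughly exchangeable correlation. HbA1c is the only outcome described as change, and protocol 4.5, 4.6 and 4.15 list no HbA1c at either pre-randomization draw. Protocol 4.11 says only that it is measured at least twice a year.

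A third tempting reading is that the methotrexate arm must show no reduction even if the drug works. That requires the full effect by the end of the run-in and the randomization sample as origin. The documents establish neither, and the planned contrast is between arms. Nor can one infer that the board's hsCRP observation was an artefact or less precise than it should have been, because the documents do not say how hsCRP was analysed.

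Finally, the mediation analysis groups participants by biomarker level reached, which needs no baseline. But the same paragraph of SAP 4.3 also speaks of reduction, which does.

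What the reply does not remove is that the samples exist, one is on drug, and the plan does not say which is baseline or that either will be used for adjustment.

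**Conclusion.** The point holds as a modest, inexpensive improvement to secondary and exploratory analyses. The randomized methotrexate-versus-placebo difference is unbiased with either baseline. Relative to a change score, one-baseline adjustment cuts variance by 25% to 15% for r of 0.5 to 0.7. About 30% is reachable only with a second, roughly exchangeable value. Both figures rest on an assumed correlation. At 3,500 per arm the practical gain is small, and it is larger within strata.

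Within-arm change and achieved reduction would be understated on methotrexate if counted from the randomization sample, by the share g of the effect already present, which is unknown. Subgroups by hsCRP at randomization would still give valid randomized comparisons, but they would sort participants by on-drug rather than untreated inflammation. The primary endpoint is unaffected.

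**What to change.** In SAP 4.3:

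- Define the effect on each biomarker as the methotrexate-versus-placebo difference at each follow-up sample, on the log scale for skewed markers such as hsCRP and IL-6.
- Estimate it by randomized arm in a repeated-measures model with visit, arm-by-visit, the SAP stratification factors and the pre-run-in value as covariates. Add the randomization value where it is assayed.
- Analyse HbA1c with its pre-randomization value as a covariate, and state when that value is measured.
- Define the pre-run-in sample as baseline for within-arm change, achieved reduction and hsCRP subgroups.
- State that methotrexate-arm change from the randomization sample will not be read as evidence for or against an effect.

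The cost is SAP wording, slightly more analysis work and possibly one more assay of samples already banked. For the banked biomarkers no new visits, draws or participants are needed. If no pre-randomization HbA1c is in fact measured, the SAP should say so and name the value that will be used.
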